10.4 HLA-INELIGIBLE PATIENTS

Patients who are not eligible for treatment with tebentafusp because of a non-HLA-eligible haplotype will be followed prospectively for clinical outcome. Patients may either be followed prospectively in real-time at the institution where this protocol is open and active and tracked in a database to monitor patient demographic, clinicopathologic, and treatment-related data. This includes age, sex, race, ethnicity, treatment history (e.g. number of prior therapies or surgeries and treatment location), date of initiation of systemic therapy, systemic therapy regimen, date of radiographic assessment, and date of progression. Radiographic assessment by RECIST 1.1 will occur in real-time or retrospectively. Patients who are treated at outside institutions will have their treatment records and scans requested for review, if permission has been granted.

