Patients who are HLA-A*02:01-negative and ineligible to receive tebentafusp will be prospectively enrolled onto a separate study arm and treated with physicians' choice of treatment. They will also be radiographically assessed at the same schedule as patients treated with tebentafusp, if feasible, and kept on this treatment arm until progression of disease or unacceptable toxicity on the physicians' choice regimen.

Maximum Total Number of Subjects

23 patients will be on treatment arm. 24 patients will be on a physician's choice arm. This equals 47 total.

Target Population

Unresectable or metastatic clear cell sarcoma patients who are HLA-A*02:01 positive.

Anticipated Length of Study (patient enrollment period, overall length including follow-up)

5 years total: 3 years of enrollment, 1 year on treatment, 1 year follow-up

Study Drug (s)

Tebentafusp

Dosing and Administration

Tebentafusp will be administered via IV infusion on Days 1, 8, and 15 of a 21-day cycle. Treatment on C1D1 will be 20mcg, treatment on C1D8 will be 30 mcg. After this initial dosing period, beginning at C1D15 and beyond, patients are eligible to receive the full dose of 68 mcg. This escalated dose administered at C1D15 will be the dose used for the remainder of the treatment period unless dose reduction is implemented for toxicity.

Efficacy Evaluations

Radiographic assessment via CT or MR (where CT is not feasible or per the investigator's discretion) will occur at baseline and every subsequent 6 weeks through 48 weeks, and then every 9 weeks thereafter (+/- 7 days on scan date).

Tumor evaluations for the purposes of the primary endpoint are made based on RECIST v1.1. The efficacy assessments and definitions of best response and PD for the purposes of the primary endpoint of ORR described in this study are based on the RECIST v1.1 (section 11.1.4).

Safety Evaluations/ Concerns

Tebentafusp is FDA-approved for HLA-A*02:01-positive adult patients with unresectable or metastatic uveal melanoma. Patients will be monitored for AEs and toxicities will be reported per CTCAEv5.

Special warnings and precautions listed in the investigator's brochure include:

- 1) Cytokine release syndrome
- 2) Rash
- 3) Elevated liver enzymes

Other clinically relevant AEs include:

- 1) Tumor flare/pain
- 2) Elevated pancreatic enzymes
- 3) Lymphopenia

Correlative Studies

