2.4 Study Design

This is a multi-center, open label, phase II study of tebentafusp in patients with unresectable or metastatic clear cell sarcoma (CCS). Patients who screen positive for the HLA-A*02:01 haplotype and meet the eligibility requirements will be treated with weekly intravenous (IV) tebentafusp in escalating doses (20 µg on day 1, 30 µg on day 8, and then 68 µg weekly thereafter).

Radiographic assessment will occur at baseline and every subsequent 6 weeks (+/- 1 week) through 48 weeks, and then every 9 weeks thereafter. Patients will be treated until progression of disease, unacceptable toxicity, or withdrawal of consent. All patients treated with tebentafusp will undergo mandatory research biopsies at baseline and on-treatment (week 6 +/- 1 week), if it is safe and feasible to do so. Serial peripheral blood samples for correlative analysis will be collected at baseline and at various time points on treatment.

Patients who are HLA-A*02:01-negative and therefore ineligible to receive tebentafusp will be prospectively enrolled onto a separate study arm and treated with physicians' choice of systemic therapy. They will also be radiographically assessed at the same schedule (if feasible) as patients treated with tebentafusp and kept on this treatment arm until progression of disease or unacceptable toxicity on the physicians' choice regimen.

The primary study objective is to estimate the proportion of patients who are progression-free at 24 weeks. Secondary objectives include estimating the overall response rate by RECIST and Choi criteria, the duration of response (DoR), the clinical benefit rate (CBR), the progression-free survival, the overall survival (OS), and describing the safety of study treatment. An additional secondary objective will be to compare the PFS of patients who are HLA-ineligible and treated with physician's choice of therapy to the HLA-A*02:01-positive population treated with tebentafusp.

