3. PATIENT SELECTION

3.1 Eligibility Criteria

- 3.1.1 Age \geq 18 years
- 3.1.2 Histologically confirmed diagnosis of HMB-45+ clear cell sarcoma which is unresectable and/or metastatic
- 3.1.3 HLA-A*02:01 positive
- 3.1.4 ECOG Performance Status of \leq 2 at screening
- 3.1.5 At least one site of measurable disease on CT/MRI scan as defined by RECIST v 1.1 criteria. Baseline imaging must be performed within 28 days of Cycle 1 Day 1 of study.
- 3.1.6 Adequate organ function within 28 days of Day 1 of study defined as:
 - Absolute Neutrophil Count (ANC) \geq 1.5
 - Platelets \geq 75
 - ALT and AST \leq 2.5 x institutional upper limit of normal (ULN) or \leq 5.0 x institutional ULN if considered due to tumor
 - Alkaline phosphatase \leq 2.5 x institutional ULN unless considered due to tumor
 - Serum bilirubin \leq 1.5 x institutional ULN. **NOTE:** Patients with elevated bilirubin secondary to Gilbert's disease are eligible to participate in the study

- Serum creatinine $\leq 1.5 \times$ institutional ULN or 24-hour creatinine clearance ≥ 50 ml/min (calculated creatinine clearance using Cockcroft formula is acceptable)
- 3.1.7 Written, voluntary informed consent
- 3.1.8 Patients must demonstrate progression of disease by RECIST 1.1 within 6 months of study enrollment. Newly diagnosed patients with unresectable or metastatic disease and only one baseline scan are eligible to screen and enroll.
- 3.1.9 All other relevant medical conditions must be well-managed and stable, in the opinion of the investigator, for at least 28 days prior to first administration of study drug

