11.1.7 Progression-Free Survival

PFS is defined as the duration of time from start of treatment to time of progression or death, whichever occurs first.

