13.4 Analysis of Secondary Endpoints

CCS is a rare tumor and approximately one-third of patients are expected to be HLA-A*02:01-positive.³⁵ As a secondary endpoint, we will compare the median PFS of patients treated with tebentafusp to historical controls, and we will leverage the HLA-ineligible CCS population to compare the median PFS of patients treated with physicians' choice of therapy to the HLA-A*02:01-positive population treated with tebentafusp. This secondary endpoint will provide a second point of comparison to historical controls. Prospectively enrolling 24 patients with CCS who are HLA-A*02:01-negative and treated with physicians' choice of therapy will provide 80% power to detect a HR of 2 at a one-sided type I error rate of 0.1 when compared to tebentafusp-treated CCS patients, respectively.

Additional secondary endpoints will be: to estimate the best ORR by RECIST 1.1 and by Choi criteria, to estimate the median duration of response among responders, to estimate the overall CBR and CBR at 12 and 24 weeks, to estimate the PFS at 12 weeks and median PFS, to estimate the median OS, and to further describe the safety as assessed by CTCAE version 5.0.

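### The HLA-negative comparator for the powered PFS comparison has no stated prognostic entry criteria and looser scan assessment, so the stated 80% power holds only under equal assessment that the protocol does not secure

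*Protocol*

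**What the plan says.** The synopsis sets the arm sizes: "23 patients will be on treatment arm. 24 patients will be on a physician's choice arm. This equals 47 total". Section 13.4 states that the 24 HLA-negative patients "will provide 80% power to detect a HR of 2 at a one-sided type I error rate of 0.1 when compared to tebentafusp-treated CCS patients". Section 11.1.7 defines the endpoint: "PFS is defined as the duration of time from start of treatment to time of progression or death, whichever occurs first".

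Entry: the only eligibility list, section 3.1, contains "3.1.3 HLA-A*02:01 positive", so it cannot govern the HLA-negative arm. Under sections 5 and 10.1.2 all patients enter pre-screening with unresectable or metastatic CCS. HLA-ineligible patients are then offered observational follow-up and do not go on to Screening.

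Scans: section 5 ties tebentafusp scans to C1D1 within 7 days and does not let them move with treatment delays, for the sake of accurate PFS. For the HLA-negative arm, section 2.4 says: "They will also be radiographically assessed at the same schedule (if feasible) as patients treated with tebentafusp". Section 10.4 adds that patients may be treated at outside institutions, whose records and scans are requested if permission was given.

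Data: after demographics and treatment history, the section 10.4 list ends, and the reading rule begins, with: "systemic therapy regimen, date of radiographic assessment, and date of progression. Radiographic assessment by RECIST 1.1 will occur in real-time or retrospectively".

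**The concern.** In a non-randomised comparison, the hazard ratio means something only if the two groups are alike at entry and their events are found in the same way. The protocol secures neither.

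ECOG status, measurable disease, recent progression, organ function, CNS disease and steroid use all filter the tebentafusp arm. None is stated for the comparator. Progression is seen only at a scan, so a longer comparator scan interval makes comparator PFS look longer. A comparator death that is not captured does the same. Both work against tebentafusp. Selection could work either way.

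What is at stake is a named secondary objective that uses 24 of the 47 patients in an ultra-rare disease. Analysis can partly repair unequal scan timing, because scan dates are collected. It cannot restore entry criteria that were never applied or a baseline ECOG that was never recorded.

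**Working it through.** **1. The plan's own figure.** Inputs from section 13.4 and the synopsis: HR 2, one-sided alpha 0.1, power 80%, 24 v 23, so the comparator share is p = 24/47 = 0.511.

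- Schoenfeld events: d = (1.2816 + 0.8416)² / [p(1−p)(ln 2)²] = 4.508 / (0.2499 × 0.4805) = 37.5, so 38 of 47.
- Power at 38 events: Φ(√(38 × 0.2499) × 0.6931 − 1.2816) = Φ(0.854) = 80.4%. The stated figure reproduces.
- Expected events: the synopsis gives "5 years total: 3 years of enrollment, 1 year on treatment, 1 year follow-up". With exponential PFS, control medians of 2.5 to 4.3 months (the CCS series in section 2.1), accrual of 2 to 4 years and 1 to 2 years of further follow-up, 42 to 47 events are expected, for a nominal power of 83–86%.

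**2. Unequal assessment (assumed inputs).** The protocol gives no comparator scan interval and no share of events that are deaths without prior progression, so both are assumptions. Log-rank simulation: 23 v 24, exponential PFS, tebentafusp scans 6-weekly to week 48 and then 9-weekly, HR 2, one-sided 0.1. Ranges within a cell reflect different assumed shares of events that are observed deaths (0 to 15%).

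| Comparator assessment | Power, control median 2.5 months | Power, control median 4 months |
|---|---|---|
| Same schedule, deaths captured | – | 83% |
| Every 9 weeks, deaths captured | 71% | 77–80% |
| Every 12 weeks, deaths captured | 57–61% | 70–72% |

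With identical scans, a 4-month median, and comparator deaths without prior progression lost (censored at the last scan):

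| Events that are such deaths | 5% | 10% | 15% | 20% |
|---|---|---|---|---|
| Power | 77% | 69% | 63% | 54% |
| False-positive rate | 7% | 5% | 4% | 2% |

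With 12-weekly scans and 15% such deaths together, power is 50%. At the 4-month median with 15% observed deaths, the false-positive rate falls from the nominal 10% to about 7% with 9-weekly and 4% with 12-weekly scans. These faults therefore hide a benefit; they do not create one.

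**3. Selection (assumed input).** Suppose tebentafusp has no effect but the comparator hazard is 1.3 times higher because of who enters. The false-positive rate is Φ(√(d × 0.2499) × ln 1.3 − 1.2816), with ln 1.3 = 0.2624:

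- d = 38: Φ(0.809 − 1.282) = 32%
- d = 45: Φ(0.880 − 1.282) = 34%
- d = 47: Φ(0.899 − 1.282) = 35%

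Simulation with scan-based detection runs slightly higher, so about 32–37% covers both. A shift the other way would reduce power instead.

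**4. Primary endpoint.** The exact Simon design (at most 1 of 13 stops; 5 of 23 is positive) has alpha 0.068 and power 0.844. It uses only the tebentafusp arm and is untouched.

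**The case against.** Much of the defence is sound.

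- **Power.** A reader might infer that the 80% is a mistake. It is not: it follows from its own inputs, with events to spare. Every shortfall above needs an assumed scan gap or death loss, and a 9-weekly interval at a 4-month median costs little.
- **Deaths.** A reader might infer that comparator deaths will not be recorded. The documents do not support that. The 10.4 list is introduced as non-exclusive. Section 4.1 says secondary-endpoint data are captured. Section 5.4 sets survival follow-up without limiting it to one arm, and section 5.5 requires the date of removal, including death, on the CRF. What stands is that death is not named where the comparator's data are specified, while the study calendar is built on tebentafusp cycles.
- **Other data.** The last progression-free date can be derived from the listed scan dates, and number of prior therapies is listed.
- **Clock.** It is largely settled by section 11.1.7 and by follow-up on the physician's-choice regimen. Section 10.4 records a start date of systemic therapy without saying which regimen, so a sentence would help.
- **Entry.** Disease and stage are shared through pre-screening, so the groups are not wholly unmatched.
- **Direction.** It is tempting to say that a frailer comparator flatters tebentafusp. Yet the recent-progression rule (3.1.8) also applies only to the tebentafusp arm and could select faster disease there.
- **Status.** Section 13.1 calls these real-world outcomes and section 13.4 a second point of comparison to historical controls. The choice of model is commonly left to an SAP. Entry criteria and baseline data capture are not.

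**Conclusion.** The point holds as one about bias and ascertainment in a secondary, non-randomised comparison, not as an error in the power calculation. The protocol attaches 80% power to a PFS comparison whose comparator has no stated ECOG, measurable-disease or recent-progression criterion, whose scan timing and reading are looser than in the tebentafusp arm, and whose data list does not name ECOG or death.

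The 80% is right for about 38 events with equal assessment. Departures within a plausible range take it to about 71–80% (9-weekly comparator scans), 57–72% (12-weekly), or about 70% (10% of events being uncaptured comparator deaths). A 1.3-fold selection effect could more than triple the false-positive rate. The scan intervals, death share and 1.3 are assumptions; the documents give no values for them and no direction for selection. Because the biases can oppose each other, neither a favourable nor a null hazard ratio could be read with confidence. The change should be made, but the primary conclusion does not depend on it.

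**What to change.** (a) In 10.4, define the PFS comparison set as HLA-negative patients who meet the prognostic criteria of 3.1 other than HLA: HMB-45-positive unresectable or metastatic CCS, ECOG 2 or less, measurable disease, and progression within 6 months or new diagnosis. Do not import the drug-safety exclusions or extra tests; applying all of 3.1 and 3.2 to an observational cohort would be costly.

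(b) State that the PFS clock starts at the first dose of the physician's-choice regimen begun after pre-screening consent.

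(c) Add ECOG, measurable disease, date of death and start of next therapy to the 10.4 data list. State that all comparator scans are read by RECIST 1.1 under the same rule as the tebentafusp arm.

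(d) In 13.4, add an interval-censored analysis using the scan dates already collected, adjusted for line of therapy and, if numbers allow, ECOG. State that the 80% refers to about 38 events with equal assessment and that the comparison is non-randomised.

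Cost: protocol wording and a few eCRF fields. Some HLA-negative patients will fall outside the comparison set, which lowers its event count; they can still be described. The interval-censored analysis addresses scan timing only; selection is limited by (a) and the adjustment, not removed.

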10.5 VITAL SIGNS

Vital signs (body temperature, pulse rate, respiratory rate, and blood pressure, oxygen saturation) must be performed before dosing, and after the tebentafusp administration as indicated in Table 3 and as per institutional standards.

Vital signs should be assessed on the scheduled day, even if study treatment is being withheld. More frequent examinations may be performed at the discretion of the investigator if medically indicated and will be recorded as unscheduled assessment.

Table 2 Tebentafusp Post-dose Vital Signs Monitoring

C1D1, C1D8, C1D15 Inpatient monitoring required for all	Vital signs monitored per institutional standards at a minimum of every 4 hours.
--	--

dosings of the first six patients; if no Grade \geq 2 CRS or Grade \geq 3 infusion-reactions are seen among the first six patients, subsequent patients can be treated as outpatients
	
Patients should be monitored for at least 16 hours after dosing. Patients experiencing grade 2 or greater hypotension at C1D15 require inpatient monitoring for the subsequent/next C2D1 dose. Those experiencing grade 3 or 4 hypotension at C1D1, C1D8, or C1D15 require hourly vital signs monitoring for a minimum of 8 hours after dosing for any doses administered as an outpatient through C3D1. Patients who are permitted to receive dose escalation treatment as an outpatient must be monitored for at least 8 hours post-end of infusion on C1D1, C1D8, and C1D15. Vital signs must be confirmed stable prior to discharge. Minimum thresholds are body temperature $<$ 38.0°C, heart rate $<$ 100 beats per minute, and oxygen saturation \geq 92% on room air. Patients should be informed to reside within a 30-minute travel distance to a local emergency room. Patients will be provided a wallet card indicating their current treatment status at the time of discharge.

C2D1 Inpatient monitoring required for exception noted
	
Patients experiencing a grade 2 or greater hypotension at C1D15 must be observed as an inpatient for C2D1 dose, with vital signs performed at a minimum of every 4 hours and monitoring for at least 16 hours after dosing.


C2D1 through C2D15 Monitoring requirements for exceptions noted
	
Patients experiencing grade 3 or 4 hypotension at C1D1, C1D8, or C1D15 require hourly vital signs monitoring for minimum of 8 hours after dosing for any doses administered as an outpatient through C3D1. If patients experienced grade \geq 2 hypotension at C1D15, they must be monitored as an inpatient for C2D1, as noted above.

C2 and later cycles- Days 1, 8, and 15 Outpatient monitoring
	
For patients without grade 2 or greater hypotension at C1D15 or grade 3 or 4 hypotension at C1D1, C1D8, or C1D15, outpatient vital signs must be monitored in

	clinic for minimum of 1 hour after infusion with at least 2 post-dose vital signs measurements performed. For patients who have received outpatient treatment with tebentafusp for at least 3 months without an interruption greater than 2 weeks, outpatient monitoring in clinic may be decreased to minimum of 30 minutes after dosing.
Treatment breaks/delays	Patients with break or delay in treatment for > 2 weeks AND with history of a grade 3 or 4 event of hypotension with tebentafusp dosing during the first weeks of treatment will be monitored as an inpatient for the dose subsequent to the break in dosing, with vital signs performed at a minimum of every 4 hours and monitoring for at least 16 hours after dosing.

STUDY CALENDAR

Procedure	Pre-screen	Screening	Cycle 1			Cycle 2	Cycle 3+	EOT	Follow-up
Day of cycle		-28to -1	1	8	15	1	1		
Informed consent	X ¹	X							
HLA typing ¹	X								
Medical history		X							
Concomitant medications		X	Continually assessed						
Physical exam ²		X	X			X	X	X	
Vital signs ³		X	X	X	X	X	X	X	
Height		X							
Weight		X				X	X	X	
Performance status		X							
Hematology panel		X	X			X	X	X	
Chemistry panel		X	X			X	X	X	
Coagulation studies		X						X	
Urinalysis		X						X	
Thyroid function ⁴		X					X (q2cycles)	X	
Pregnancy test ⁵		X					X	X	
Radiographic evaluation ⁶		X					X (q9weeks)		
EKG		X							
Adverse events			Continually assessed						
Biopsy ⁷		X					X	X (optional)	
Research blood ⁸		X				X	X	X	
Tebentafusp ⁹			X	X	X	X	X		
OS assessment ¹⁰									X

1 HLA status will be determined during the pre-screening period. Patients should not sign the Main Study Consent Form and enter Screening until the results of the central assay in Pre-Screening is known.

2 At screening and C1D1, prior to dosing, a complete physical examination will be completed. From C1D8 onwards, a short physical examination will be performed. Starting with C4D1, patients will have short physical examination performed only on day 1 of the cycle and at EOT

3 Inpatient hospitalization and frequent vital signs (at a minimum of every 4 hours [\pm 30 min] or more frequently according to institutional standards) are required at C1D1, C1D8, and C1D15. Inpatient monitoring at Cycle 2 Day 1 and beyond will be determined based on the toxicity observed in the individual patient in C1D1-C1D15. Patients experiencing a grade 2 or greater hypotension event at C1D15 must be observed as an inpatient for the subsequent C2D1 dose.

4 Thyroid function studies to be completed on Day 1 of every odd-numbered cycle at Cycle 3 and beyond, as well as at EOT

5 Pregnancy testing required every 6 weeks and at EOT in all WOCBP

6 Radiographic assessment via CT or MR (where CT is not feasible or per the investigator's discretion) will occur at baseline and every subsequent 6 weeks through 48 weeks, and then every 9 weeks thereafter. Progression of disease by RECIST 1.1 within 24 weeks is required for enrollment, unless the patient has a new diagnosis of CCS.

7 Mandatory biopsies are required at baseline within 28 days of study initiation and again after two cycles of treatment at C3 (+/- 7days). Biopsy at progression will be optional.

8 Research blood will be collected at baseline (during study screening or on C1D1 prior to initiating treatment), C2D1, C3D1, C5D1, C9D1, and end of treatment.

9 Tebentafusp will be administered on the scheduled day (\pm 2 days), and consecutive infusions of tebentafusp must be administered at least 5 days apart.

10 Survival follow-up should be completed every 12 weeks until death or until the end of the study is reached.

